The modified Skindex-16 (GL-QoL) Emotional and Functioning domain and overall scores will be derived in accordance with the Skindex-16 manual, adapted for the GL-QoL. The scores will be standardized on a scale from 0 (no impact) to 100 (maximal impact); a scale score is the average of responses to items addressing a construct. Domain and overall scores will be calculated if at least two of each of three domain items are present. The absolute change from baseline (measured on the screening visit) will be calculated for the domain and overall scores and statistically compared between the treatment groups using the Wilcoxon Rank Sum test (or t-test). Estimates of ‘mild’, ‘moderate’, and ‘severe’ psychological impact, and of the minimal clinical important difference, will be used to aid interpretation of scores.

The analysis will be conducted with respect to the hierarchical order of key secondary endpoints; the analysis using the Emotional domain first, the Functioning domain second, and the overall score third. All analyses will be conducted on observed values only, i.e. missing domain and overall scores will be excluded from analysis; no imputation of missing domain and overall scores will be performed.

Concerns Relating to Glabellar Lines

The FACE-Q Appraisal of Lines Between Eyebrows scale and FACE-Q Age Appraisal VAS scores will be derived in accordance with the developers’ instructions and missing data treated accordingly. The absolute change from baseline (measured

on the screening visit) will be calculated for each scale and statistically compared between the treatment groups using the Wilcoxon Rank Sum test. All analyses will be conducted on observed values only, i.e. missing scale scores will be excluded from analysis; no imputation of missing scores will be performed. This analysis will be conducted with respect to the hierarchical order of key secondary endpoints as well; the analysis of FACE-Q Appraisal of Lines Between Eyebrows scale first, followed by the analysis of FACE-Q Age Appraisal VAS scores.

Exploratory Analyses

Exploratory analyses of modified Skindex-16 (GL-QoL) domain and overall score and FACE-Q Appraisal of Lines Between Eyebrows scale and FACE-Q Age Appraisal VAS will also be conducted using the MFAS and the PP population. Subgroup analysis by geographic region, country, and site, or by subjects with previous use of botulinum toxin versus naïve subjects will not be conducted.

Additional Secondary Analyses:

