3.2 Randomization and blinding

3.2.1 Randomization

This is a randomized, double blind, placebo-controlled efficacy and safety clinical study followed by an open label extension. Subjects will be randomly assigned to receive either BoNT/A-DP or placebo at a ratio of 3:1 respectively in the first treatment cycle. The 3:1 ratio in favor of active treatment versus placebo has been selected to increase the safety data base size.

Randomization will be performed per study site via interactive web response system (IWRS). One unique randomization code will be assigned to each subject.

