8 STATISTICAL METHODS

8.1 General statistical conventions

All statistical procedures will be completed using SAS version 9.3 or higher.

The statistical analysis of the first treatment cycle and the open label extension phase (cycles 2-4) will be performed after database lock of all data up to the end of the study (can take place in four-weekly intervals from study week 48 until study week 60) and final unblinding.

The statistical testing of the primary endpoint as well as the key secondary endpoints will be one-sided and will be performed using a significance (alpha) level of 0.025. A two-sided McNemar test (using a significance level of 0.05) will be used to compare the response proportions between week 4 re-treatment visit and at the preceding end of the cycle visit. This endpoint will be separately analyzed for each open label extension cycle. Two-sided 95% CIs will be provided when relevant.

Continuous variables will be summarized using descriptive statistics, including number of subjects (n), mean, standard deviation (SD), median, minimum and maximum. One additional decimal point for mean and median and two additional decimal points for SD will be used in addition to the number of decimal points used for the measured values.

For categorical variables, summaries will include counts of subjects and percentages in corresponding categories. Percentages will be rounded to one decimal place.

For statistical analyses “baseline” refers to the last observation before treatment, i.e. pre-treatment values measured on the treatment day (baseline visit, day 0), and if missing or not evaluated, values from screening visit will be used.

All summaries will be presented by treatment group, unless otherwise specified.

Analyses will be performed by visit, irrespective of any time window deviations.

All subject data, including those derived, will be presented in individual subject data listings. Unless otherwise stated, unscheduled visit results will be included in date/time chronological order, within patient listings only. All listings will be sorted by investigational site, patient number, date/time and visit. The treatment group will be stated on each listing. Unless otherwise stated, data listings will be based on the Safety Analysis Set. A listing with demographic data for screening failures will be presented.

Statistical Analysis Plan (SAP)

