8.6.1.1 Multiplicity

The testing of the primary and the five key secondary efficacy endpoints will be performed with appropriate multiplicity control based on the FAS population. The results of each test result will only be considered confirmative if the previous test in the order showed a confirmatory result at a one-sided significance level of 0.025. If the one-sided p-value is larger than 0.025 for any of the tests, the results of the subsequent tests will only be considered exploratory, and not confirmatory. The application of this hierarchical approach keeps the global significance level to 0.025 one-sided and requires no further adjustment of the significance level.

The following order of tests will be applied:

- Primary endpoint (composite endpoint)
- Key secondary endpoint 1 (composite endpoint)
- Key secondary endpoint 2 (composite endpoint)

Statistical Analysis Plan (SAP)

- Key secondary endpoint 3
 - 3.1: The investigator's in-clinic assessments
 - 3.2: The subject's in-clinic assessments
- Key secondary endpoint 4 (composite endpoint)
- Key secondary endpoint 5
 - 5.1: The modified Skindex-16 (GL-QoL) Emotional domain
 - 5.2: The modified Skindex-16 (GL-QoL) Functioning domain
 - 5.3: The modified Skindex-16 (GL-QoL) Overall score
 - 5.4: The FACE-Q Appraisal of Lines Between Eyebrows scale
 - 5.5: The FACE-Q Age Appraisal VAS score

All other analyses (e.g., additional analyses of the primary and the five key secondary efficacy endpoints using other analysis populations or other statistical methods, analyses of additional secondary endpoints) will only be considered exploratory.

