Analysis of key secondary endpoint 5: The extent of change in psychological impact (emotional and social functioning, and concerns relating to glabellar lines) at week 4 after the first treatment, in the BoNT/A-DP group in comparison with placebo, relative to baseline, as assessed by the modified Skindex-16 (GL-QoL) and the FACE-Q Appraisal of Lines Between Eyebrows and FACE-Q Age Appraisal VAS.

The modified Skindex-16 (GL-QoL) and FACE-Q Appraisal of Lines Between Eyebrows scale and FACE-Q Age Appraisal VAS scales will be analyzed according to the foreseen analysis approach of these tools, as described below.

Statistical Analysis Plan (SAP)

Emotional and Social Functioning

The modified Skindex-16 (GL-QoL) Emotional and Functioning domain and overall scores will be derived in accordance with the Skindex-16 manual, adapted for the GL-QoL. The scores will be standardized on a scale from 0 (no impact) to 100 (maximal impact); a scale score is the average of responses to items addressing a construct. Domain and overall scores will be calculated if at least two of each of three domain items are present. The absolute change from baseline (measured on the screening visit) will be calculated for the domain and overall scores and statistically compared between the treatment groups using the Wilcoxon Rank Sum test or t-test, if appropriate. Estimates of 'mild', 'moderate', and 'severe' psychological impact, and of the minimal clinical important difference, will be used to aid interpretation of scores and will be considered exploratory.

The analysis will be conducted with respect to the hierarchical order of key secondary endpoints; the analysis using the Emotional domain first, the Functioning domain second, and the overall score third. All analyses will be conducted on observed values only, i.e. missing domain and overall scores will be excluded from analysis; no imputation of missing domain and overall scores will be performed.

Concerns Relating to Glabellar Lines

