The FACE-Q Appraisal of Lines Between Eyebrows scale and FACE-Q Age Appraisal VAS scores will be derived in accordance with the developers' instructions and missing data treated accordingly. The absolute change from baseline measured on the screening visit will be calculated for the FACE-Q Appraisal of Lines Between Eyebrows scale and for the FACE-Q Age Appraisal VAS score and statistically compared between the treatment groups using the Wilcoxon Rank Sum test. All analyses will be conducted on observed values only, i.e. missing scale scores will be excluded from analysis; no imputation of missing scores will be performed. This analysis will be conducted with respect to the hierarchical order of key secondary endpoints as well; the analysis of FACE-Q Appraisal of Lines Between Eyebrows scale first, followed by the analysis of FACE-Q Age Appraisal VAS scores.

Exploratory Analyses

Exploratory analyses of modified Skindex-16 (GL-QoL) domain and overall score and FACE-Q Appraisal of Lines Between Eyebrows scale and FACE-Q Age Appraisal VAS will also be conducted using the MFAS and the PP population. The analyses described in the two previous sections will be repeated for these populations.

Statistical Analysis Plan (SAP)

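### Key secondary endpoints 5.1 to 5.5 are tested on raw change without baseline or site adjustment, and for 5.1 to 5.3 the confirmatory test is not fixed

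*SAP*

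**What the plan says.** SAP 8.6.1.1 puts 5.1 to 5.5 at the end of a fixed sequence: GL-QoL Emotional, Functioning and overall scores, then FACE-Q Appraisal of Lines Between Eyebrows, then FACE-Q Age Appraisal VAS. The rule is "If the one-sided p-value is larger than 0.025 for any of the tests, the results of the subsequent tests will only be considered exploratory". Under SAP 8.1, the primary and key secondary tests "will be one-sided and will be performed using a significance (alpha) level of 0.025".

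For 5.1 to 5.3, SAP 8.6.3 takes the absolute change from the screening score, to be "statistically compared between the treatment groups using the Wilcoxon Rank Sum test or t-test, if appropriate". Protocol 12.4.2 puts the t-test in brackets, "using the Wilcoxon Rank Sum test (or t-test", and also gives no rule. For the two FACE-Q scales (5.4 and 5.5) the SAP names one test: the change is "statistically compared between the treatment groups using the Wilcoxon Rank Sum test. All analyses will be conducted on observed values only".

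None of the five analyses has a baseline covariate or a site term. The surrounding design is as follows:
- Randomization is done per site (SAP 3.2.1).
- The primary test is a Cochran-Mantel-Haenszel test stratified by site, with small sites combined (SAP 8.6.2).
- Both instruments are completed at screening (protocol 9.3, Table 9-1), and a GL-QoL score above zero on either subscale is an entry criterion (protocol 7.1).
- SAP 8.6.3 states which p-value counts in the hierarchy for key secondary endpoints 2 to 4. It makes no such statement for endpoint 5.

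**The concern.** There are two separate issues.

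**Open test.** A confirmatory step needs one p-value that is identified before treatment codes are known. For 5.1 to 5.3 two tests are allowed, and the documents do not say what makes one of them appropriate, who decides, or when. SAP 8.1 places the analysis after database lock and final unblinding, so nothing in the text prevents the choice from being made with results in view. Test 5.1 also gates 5.2 to 5.5, so the choice can decide whether the FACE-Q tests are reached as confirmatory. Protocol 9.4.2 says the patient-reported instruments are meant to support labelling claims.

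**No adjustment.** A change score subtracts baseline with a fixed coefficient of 1. Unless the follow-up score regresses on baseline with slope 1, this leaves variance in the comparison that the collected data could remove. The entry criterion makes dependence on the starting value likely: a subject may enter with a score of zero on one of the two domains and then cannot improve on it.

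**Working it through.** **The plan's own figures.** The documents give no power, SD or effect size for endpoint 5. The sample size rests on the primary endpoint (60% vs 10%, one-sided 0.025, 90% power, 3:1), and its minimum reproduces: exact Fisher power is 89.3% at 39 + 13 and 91.6% at 42 + 14. The planned 525:175 with the stated 10% drop-out gives 525 × 0.9 = 472.5 and 175 × 0.9 = 157.5, so about 472:158.

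**Error rate of an open choice.** 40,000 null trials per distribution at 472 vs 158, one-sided 0.025, Monte Carlo SE 0.08 points. The normality rule picks the t-test or Wilcoxon from data centred within arm, so it ignores the treatment difference.

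| Distribution of change | t-test | Wilcoxon | Normality rule | Smaller p of the two |
|---|---|---|---|---|
| Normal | 2.56% | 2.55% | 2.56% | 3.06% |
| Heavy-tailed (t, 3 df) | 2.41% | 2.44% | 2.44% | 3.60% |
| Skewed (exponential) | 2.32% | 2.53% | 2.53% | 3.44% |
| Discrete 0–100 score change | 2.49% | 2.47% | 2.48% | 2.97% |

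Either test fixed in advance, or a choice by a rule blind to the treatment effect, stays near 2.5%. Only selection on the result raises the error, to about 3.0–3.6%. The case closest in form to GL-QoL is the lowest.

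**Cost of not adjusting.** Take equal SDs at screening and week 4 (set to 1), within-arm correlation rho, and the same slope in both arms.
- Variance of change: 2(1 − rho).
- Residual variance with ANCOVA: 1 − rho².
- Ratio: (1 − rho²) / [2(1 − rho)] = (1 + rho)/2, i.e. 0.60, 0.65, 0.75, 0.85 and 0.95 at rho 0.2, 0.3, 0.5, 0.7 and 0.9.

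Power is Φ(d/SE − 1.96), with SE² = variance × (1/472 + 1/158) = variance × 0.008448. Worked case, rho 0.3 and d = 0.3 SD:
- Change: SE = √(1.4 × 0.008448) = 0.1088; 0.3/0.1088 − 1.96 = 0.80; power 79%.
- ANCOVA: SE = √(0.91 × 0.008448) = 0.0877; 0.3/0.0877 − 1.96 = 1.46; power 93%.

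Power, change score → ANCOVA (rho and d are assumed):

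| rho | d = 0.2 SD | d = 0.3 SD | d = 0.5 SD |
|---|---|---|---|
| 0.2 | 41% → 60% | 73% → 92% | 99% → ~100% |
| 0.3 | 45% → 63% | 79% → 93% | 99.6% → ~100% |
| 0.5 | 59% → 71% | 90% → 97% | ~100% both |
| 0.7 | 80% → 86% | 98.8% → 99.5% | ~100% both |
| 0.9 | 99.8% → 99.9% | ~100% both | ~100% both |

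The largest gain is 60.3 − 40.5 = 19.8 points; the smallest is close to zero.

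**Against the Wilcoxon test itself.** The table uses a normal-theory test of change, whereas the SAP names Wilcoxon first. A simulation on bounded, discrete 0–100 scores at 472:158 with an assumed 0.25 SD difference gave about 60% (Wilcoxon on change) vs 81% (ANCOVA) at rho 0.3, 73% vs 87% at 0.5, and 90% vs 96% at 0.7. The type I error of ANCOVA was 2.3–2.8%, so the gain does not depend on normal data.

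**The case against.** **The documents lean towards Wilcoxon.** It is named first in both, the SAP's general list of efficacy tests (8.6.1) includes it and omits the t-test, and 5.4 and 5.5 use it alone. The wording can be read as an ordinary assumption check, which would keep the error near 2.5%. Table templates are in a separate document that might settle the matter. This makes a benign choice plausible. It still does not name the p-value, and a confirmatory sequence should not rest on inference.

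**Stronger readings are not supported.** A reader might infer that the plan runs these tests above 2.5%. It does not: that requires computing both tests after unblinding and keeping the better one, which no section proposes. A reader might also infer that the missing adjustment inflates error. Under randomization it does not, and ignoring site after per-site randomization tends to be conservative. Nor does the open choice extend to the whole of endpoint 5, since 5.4 and 5.5 have a single named test.

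**An unadjusted change score is valid.** This is correct. Baseline is subtracted, so it is not ignored, and at a 0.5 SD difference both analyses have at least 99% power. The argument for adjustment is efficiency at no data cost, and its size rests on assumed inputs. SAP 8.6.3 also says the scales follow the analysis approach foreseen for those tools, which cannot be checked here. That is a reason to allow a rank-based adjusted analysis as an alternative to ANCOVA.

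**Conclusion.** The point holds in two parts. For 5.1 to 5.3 the SAP does not fix the test that enters the hierarchy, so its statement that the procedure holds one-sided 0.025 is not assured for these steps. The exposure is about 3.0–3.6% if the smaller p-value is selected after unblinding, and none if the test is fixed beforehand.

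For all five tests, the analysis omits a screening covariate and site although both are available. This is lost power only. The variance ratio (1 + rho)/2 assumes equal SDs and a common slope. The gain of nearly nil to about 20 points assumes rho of 0.2 to 0.9, differences of 0.2 to 0.5 SD and 472:158 evaluable; week 4 losses may be smaller than the overall 10% drop-out.

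The five tests come last and are confirmatory only if the primary endpoint and key secondary endpoints 1, 2, 3.1, 3.2 and 4 have all succeeded. None of those endpoints is affected. The change should be made, and it has value only before unblinding.

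**What to change.** In SAP 8.6.3, before unblinding:
- Delete the t-test alternative for the GL-QoL scores.
- For each of 5.1 to 5.5, name the single one-sided p-value that enters the hierarchy, in the way the SAP already does for key secondary endpoints 2 to 4.
- Take that p-value from an analysis of week 4 change adjusted for the screening score of the same scale and for site, with small sites pooled as for the primary test. This can be ANCOVA or a rank-based equivalent; choose one and write it down.
- Keep a site-stratified Wilcoxon (van Elteren) test as a sensitivity analysis.
- Record the departure from protocol 12.4.2 in SAP section 9.

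If the sponsor does not want adjustment, deleting the t-test alternative alone closes the error-rate gap and aligns 5.1 to 5.3 with 5.4 and 5.5, but leaves the power loss.

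The cost is SAP wording, one section 9 entry and a few lines of code. No new data are needed.

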8.6.4 Additional secondary analyses

The additional secondary efficacy endpoints will be analyzed applying the appropriate statistical method for the comparison of both treatment arms. For proportions

- of responders with a FWS score of 0 or 1 and an improvement ≥ 2 points in FWS score at maximum frown,
- of subjects with ≥ 2 point reduction in FWS at maximum frown,
- of subjects with a ≥ 1 point reduction in FWS at rest, and
- of subjects with an improvement of ≥ 2 points in FWS at maximum frown at 4 weeks after re-treatment,

the Cochran-Mantel-Haenszel test (with stratification variable site) and the Pearson χ^2 -test will be applied. In case of a total number of observations below 30, or in case of at least one cell frequency below 5, Fisher's exact test will be used instead of the χ^2 -test. Two-sided 95% CIs for response rates will be calculated, where appropriate. Additionally the cumulative proportions of effects at weeks 1, 2, and 4 will be calculated. Time to onset of effect in the first treatment cycle will be analyzed descriptively and by using the Kaplan-Meier method. Moreover, the daily assessments of the line severity when frowning will be analyzed descriptively. The FACE-Q satisfaction with outcome scale will be analyzed descriptively.

All endpoints, with exception of “responder” 4 weeks after re-treatment, will be analyzed for the first treatment cycle only. The analysis of “responder” 4 weeks after re-treatment will be conducted on observed values only, i.e. subjects with missing investigator or the subject in-clinic assessments on FWS week 4 or at the preceding end of the cycle visit will be excluded from analysis. Subjects who were treated with placebo during the first treatment cycle are excluded from the analysis of this endpoint, but not assigned as being non-responders. A two-sided McNemar test (using a significance level of 0.05) will be used to compare the response proportions between week 4 re-treatment visit and at the preceding end of the cycle visit. This endpoint will be separately analyzed for each open label extension cycle.

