3.1 General study design

This multicenter Phase 3 study is comprised of two parts. The first part of the study is a randomized, double blind, placebo-controlled, phase which aims to demonstrate efficacy and safety of BoNT/A-DP compared with placebo. The second part is an open label extension phase to evaluate efficacy after repeat treatments and long term safety.

Subjects can receive a maximum of four treatment cycles over the duration of the study, a single treatment in the first cycle compared with placebo, and up to three subsequent treatments in the open label extension study.

Adult subjects less or equal 75 years old with moderate to severe glabellar frown lines at maximum frown with an important psychological impact as indicated by scores >0 on either the Emotional or Functioning subscales of the modified Skindex-16 (GL-QoL) will be enrolled in this study. Approximately 18 sites (50% in EU and 50% in US) will enroll in total 700 evaluable subjects. Applying a 10% drop out rate will result in a total number of completing subjects of about 630.

The overall study scheme is presented below:

[figure not shown]

The duration of study participation for each subject will be up to 14 calendar days of screening followed by 48 to 60 weeks of treatment (re-screening will not be permitted). The first treatment cycle will be a double blinded cycle followed by up to three open label treatment cycles. Each cycle will be at least 12 weeks and can be prolonged in 4-week increments, depending on treatment effect. Re-treatment is possible until study-week 48.

[figure not shown]
Statistical Analysis Plan (SAP)

Visit Scheme/Treatment Cycle 1 (double blind)

Visit Scheme/Treatment Cycles 2, 3, 4 (open label)

Statistical Analysis Plan (SAP)

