4.3 Additional Secondary endpoints

The additional secondary endpoints of this study are:

6. The proportion of responders among BoNT/A-DP and placebo groups with a FWS score of 0 or 1 and an improvement ≥ 2 points in FWS score (at maximum frown) during the first treatment cycle visit relative to baseline, based on both the investigator's and the subject's in-clinic assessments (composite endpoint, at weeks 1, 2 and 8).

Statistical Analysis Plan (SAP)

7. The proportion of subjects with ≥ 2 point reduction in FWS score (at maximum frown) in the BoNT/A-DP and placebo groups during the first treatment cycle visit relative to baseline, based on the independent rater's assessment of photographs (at baseline and visits 2, 4, 12, 16 and 20 weeks after treatment, within the first treatment cycle).
8. Time to onset of effect in the BoNT/A-DP and placebo groups in the first treatment cycle, as measured at weeks 1, 2 and 4 based separately on subject and investigator assessments. Onset of effect defined as at least a 1 point improvement in FWS score from baseline (at maximum frown). In addition, onset of effect will be assessed by subjects daily in the first 2 weeks after treatment, by recordings in the subject diary.
9. The extent of subject perceptions of effect of, and satisfaction with, treatment, in the BoNT/A-DP and placebo groups, during each treatment cycle, as assessed by the FACE-Q Satisfaction with Outcome Scale.
10. The proportion of subjects with a ≥ 1 point reduction in FWS score at rest in the BoNT/A-DP and placebo groups, relative to baseline, during the first treatment cycle, based on the independent rater's assessment of photos.
11. The percentage of subjects with a FWS score of 0 or 1 and an improvement of ≥ 2 points in FWS score at maximum frown (investigator and subject assessment) at four weeks after re-treatment relative to the rating at the preceding end of cycle visit.

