8.6.2 Analysis of primary efficacy endpoint(s)

Primary Analysis:

The proportion of subjects (responders) meeting the primary endpoint with a FWS score of 0 or 1 and an improvement ≥ 2 points in FWS score (at maximum frown) at week 4 visit relative to baseline, based on both the investigator and the subject in-clinic assessments will be analyzed using the Cochran-Mantel-Haenszel test with stratification variable site using a significance level (α) of 0.025. Small sites with less than 3 placebo subjects will be combined. The null hypothesis H_0 given below will be tested against the alternative hypothesis H_1 :

$$H_0: p_{BoNT/A-DP} \leq p_{Placebo}$$

$$H_1: p_{BoNT/A-DP} > p_{Placebo}$$

The Cochran-Mantel-Haenszel test will be applied by the SAS procedure Proc Freq using the General Association Statistic. The one-sided p-value will be derived by halving the two-sided p-value delivered by the SAS procedure. Superiority of BoNT/A-DP over placebo will only be concluded if, besides statistical significance (one-sided p-value

Statistical Analysis Plan (SAP)

≤ 0.025), the proportion of responders in the BoNT/A-DP treatment group is higher than for the placebo treatment group.

The FAS will serve as the primary analysis set.

Subjects with missing investigator or subject in-clinic assessments with the FWS at baseline or visit week 4 will be assigned as being non-responders.

Additional Exploratory Analyses on the Primary Endpoint Variable:

Further analyses on the primary endpoint variable are exploratory. A one-sided Pearson χ^2 -test will be applied. Two-sided CI of 95% for the responder rates in the BoNT/A-DP and the placebo treatment groups will be calculated using Wilson scores. As a sensitivity analysis for the primary endpoint, a tipping point analysis will be performed. Each missing value will be assigned to either a response or non-response, so that all possible combinations of replacing one or more missing values within each treatment group will be analyzed. P-values will be calculated for each combination and graphically displayed using a scatter plot.

The CIs will also be calculated for the additional analyses as listed in the following:

- The primary endpoint measure using the observed values only, i.e. missing investigator or the subject in-clinic assessments with the FWS at baseline or week 4 visit will be excluded from analysis but not assigned as being non-responders. This analysis will be performed for the FAS, MFAS and PP populations.

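### Response after re-treatment is planned on observed values only; add a version that counts a missing week 4 rating as non-response, as cycle 1 does

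*SAP*

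**What the plan says.** **Cycle 1, week 4** (SAP 8.6.2; protocol 12.4.1). The primary analysis in the FAS states: "Subjects with missing investigator or subject in-clinic assessments with the FWS at baseline or visit week 4 will be assigned as being non-responders". Observed-values, LOCF and tipping point analyses are added as exploratory work. The first is described as "The primary endpoint measure using the observed values only", with confidence intervals, and the SAP adds: "This analysis will be performed for the FAS, MFAS and PP populations".

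**Week 4 after re-treatment, endpoint 11** (SAP 7.2.1 and 8.6.4; protocol 12.4.2). The responder analysis "4 weeks after re-treatment will be conducted on observed values only, i.e. subjects with missing investigator or the subject in-clinic assessments" at week 4 or at the preceding end-of-cycle visit are excluded. Neither document attaches a missing-as-non-response version to this endpoint.

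**What else defines endpoint 11.**
- Improvement is judged "after re-treatment relative to the rating at the preceding end of cycle visit" (SAP 4.3), not against study baseline.
- "Subjects who were treated with placebo during the first treatment cycle are excluded from the analysis of this endpoint" (SAP 8.6.4).
- "A two-sided McNemar test (using a significance level of 0.05) will be used to compare the response proportions" at week 4 and at the preceding end-of-cycle visit, separately for each open-label cycle (SAP 8.6.4).
- Additional secondary endpoints are exploratory and stand outside the testing hierarchy (SAP 8.6.1.1).

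**Role of the extension** (SAP 3.1). "The second part is an open label extension phase to evaluate efficacy after repeat treatments and long term safety". SAP 8.6.4 confines every other additional secondary endpoint to the first cycle, and the key secondary endpoints also belong to cycle 1. Endpoint 11 is therefore the only planned responder result for repeat treatment.

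**The concern.** One responder definition (score 0 or 1, at least 2 points better, by both raters, at week 4) carries two missing-data rules, and neither document explains the difference. The stricter rule applies to the first injection and the more lenient one to later injections.

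Re-treatment requires an end-of-cycle score of at least 2 from both raters, so that rating should be present. In practice the subjects removed are those who were re-injected and then lack one or both week 4 ratings. Some of them are known failures: response needs success from both raters, so one failing rating settles the matter even when the other is missing. No partly rated subject can be a known success.

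At stake is how the repeat-treatment rate is read. It bears on a stated purpose of the extension, and a reader will naturally place it next to the primary cycle 1 rate.

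**Working it through.** **Inputs.** Response p = 60% on BoNT/A-DP and whole-study drop-out of 10% (SAP 5). The share m of re-treated subjects without a complete week 4 rating is not given for any cycle. I assume 2%, 5% and 10%, with 10% as an upper illustration only.

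**The plan's own figures.** The documents state no figure for this gap. The sample size that supplies the 60% does reproduce: for 60% vs 10%, 3:1 and one-sided 0.025, exact Fisher power is 91.6% at 42 + 14 = 56 subjects and 89.3% at 39 + 13. Also 700 × 0.9 = 630, as stated.

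**Step 1: effect of the rule.** Let p be the response among subjects with both ratings.
- Observed-values rate = p
- Missing-as-non-response rate = p × (1 − m)
- Gap = p × m, which is never negative

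| m | Missing = non-response | Observed values | Gap |
|---|---|---|---|
| 2% | 58.8% | 60.0% | 1.2 points |
| 5% | 57.0% | 60.0% | 3.0 points |
| 10% | 54.0% | 60.0% | 6.0 points |

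In counts, for a group the size of the active arm with m = 10%: 525 × 0.9 = 472.5 rated and 0.6 × 472.5 = 283.5 responders. Then 283.5/525 = 54.0% and 283.5/472.5 = 60.0%.

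**Step 2: one rule in both cycles.** With equal p and m, missing-as-non-response in both cycles gives 58.8%, 57.0% or 54.0% in each, a gap of 0. Observed values in both give 60% in each, also a gap of 0. The second pairing is already available, because the cycle 1 observed-values analysis is planned. The first is not.

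**Step 3: can another rating fill the hole?** The open-label week 1 visit has no FWS and week 2 is a telephone call (protocol 2.1). A subject who discontinues has an End of Study visit with FWS within one week, but protocol 9.5 records it under the termination visit. Analyses are by visit (SAP 8.1), so it does not become the week 4 rating.

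**Step 4: the McNemar test.** An end-of-cycle visit needs a score of at least 2 from both raters (SAP 3.3), so response there is zero by definition. Counting missing week 4 ratings as failures adds only pairs with non-response at both visits, and the p-value does not change. The test also says little: 6 responders against 0 already give an exact p of 0.031. The informative output of endpoint 11 is the rate with its interval, which is what the missing-data rule moves.

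**The case against.** The strongest reply is that a fair comparison is already possible. Cycle 1 week 4 is planned on observed values with confidence intervals, no cross-cycle test is planned, endpoint 11 is exploratory and uncontrolled, and both documents state its rule openly and consistently. All of this stands. It does not supply the other pairing: the primary cycle 1 rate has no re-treatment counterpart under the same rule.

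Three stronger readings are tempting, and the documents do not support them.

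- *That repeat treatment will look better than first treatment with no change in drug effect.* The rates differ in more than the missing-data rule. Endpoint 11 uses a new reference rating, so a subject who returns at score 2 must reach 0, and only active-first subjects who relapsed and agreed to re-treatment enter it. As a pure assumption, take 70% response from score 3 and 30% from score 2, with the share at score 3 falling from 75% to 60%. The rate then moves from 0.75 × 70% + 0.25 × 30% = 60% to 0.60 × 70% + 0.40 × 30% = 54%, which cancels the whole 6 points. The net direction between cycles is unknown.
- *That the true rate is overstated by 1/(1 − m), or 2% to 11%.* This needs every missing subject to be a failure. If the true rate in all re-treated subjects is 60% and the missing 10% respond at rate q, the observed-values rate is (0.60 − 0.10q)/0.90: 66.7% at q = 0, 60.0% at q = 0.6 and 56.7% at q = 0.9. Missing-as-non-response is a conservative convention, not the truth.
- *That subjects who leave vanish from the report.* Open-label disposition and withdrawal reasons are tabulated (SAP 8.2), and adverse events leading to discontinuation are shown by cycle (SAP 8.7.2). What is lost is their place in the responder denominator.

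The 10% is also spread over up to 60 weeks, and late week 4 visits still count because time windows are ignored in the analysis. Loss within four weeks of one injection may well be smaller.

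**Conclusion.** The point holds in a limited form. The only planned repeat-treatment responder rate leaves out re-injected subjects without a complete week 4 rating, including some who are certain non-responders. On the same data it can only equal or exceed the rate under the cycle 1 primary rule. The difference is p × m: 1.2 to 6.0 points at 60% response and 2% to 10% missing, and nothing if no rating is missing. Both the per-cycle missing share and the carrying over of 60% to later cycles are assumptions.

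Set beside the primary cycle 1 rate, repeat-treatment efficacy can therefore look better because of the rule alone. No confirmatory conclusion is touched and the McNemar p-value is unaffected. This is a cheap improvement in reporting, not a flaw in the main inference.

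**What to change.** In SAP 7.2.1 and 8.6.4 (matching protocol 12.4.2, or listed as a change in SAP 9):

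1. For each open-label cycle, pre-specify endpoint 11 in all re-treated subjects who received active treatment first, with a missing week 4 investigator or subject rating counted as non-response.
2. Report it beside the observed-values result, with the number of subjects missing a week 4 rating in that cycle.
3. State that any display of response across cycles uses the same missing-data rule in every cycle.

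The cost is SAP wording and one extra run per open-label cycle, with no new data. The only downside is that the added rates will be slightly less favourable wherever ratings are missing. The new version will not make the cycles fully comparable, because the changed reference rating and selection into re-treatment remain; a footnote to any joint table should say so.
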